13.1.3 Number of days without oxygen use

Number of days without oxygen use during the study (Baseline to Day 28) will be summarized as a continuous variable by treatment. An estimate of the difference in mean numbers of days between SIR1-365 dose and placebo will be provided along with a corresponding 95% CI based on an ANOVA model with treatment as fixed effect.

The continuous duration (in days) where a patient's oxygen requirement is 'Room Air' will be derived using the date and time information from the 'O₂ Saturation' and 'Changes in Patient O₂ Requirements' eCRFs to calculate the cumulative days (including fractional days) on 'room air' through the end of calendar Day 28 where Day 1 is the day of the first dose of SIR1-365/matching placebo (or date of randomization if not treated). In the event that days/time on only room air are available after the end of day 28 that time (beyond the interval of interest) will not be included in the oxygen-free days.

The above analysis will also be repeated Baseline to Day 14.

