#### **8.1.1. $\text{PaO}_2/\text{FiO}_2$ ratio**

$\text{PaO}_2/\text{FiO}_2$  ratio will be evaluated by blood gas analyzer at screening for eligibility determination, within 30 minutes before dosing on Day 1 as baseline, and within 30 minutes after 2nd dose on Day 7 and Day 14. Change from baseline to Day 7 and to Day 14 on  $\text{PaO}_2/\text{FiO}_2$  ratio will be one of the secondary efficacy measures in this study.

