***Number of days without oxygen use***

Number of days without oxygen use during the study (Baseline to Day 28) will be summarized as a continuous variable by visit and treatment. An estimate of the difference mean numbers of days will be provided along with a corresponding 95% CI based on a 1-way ANOVA model with a single term for treatment. The definition of a “day”, such as calendar day versus a 24 hours period, will be defined in the SAP.

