7 RANDOMIZATION

Patients will be randomized to one of the 2 treatment groups: SIR1-365 100 mg or placebo at a 1:1 ratio. Randomization will be stratified according to age group (2 levels: < 60 or \geq 60 years), Dexamethasone use (2 levels: Yes or No), and Remdesivir use (2 levels: Yes or No).

Randomization will be controlled by a web-based Randomization and Trial Supply Management (RTSM) system.

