12.2 Adjustments for Covariates

Baseline measurement of the respective dependent variable will be used as a covariate in analysis of covariance (ANCOVA) models for selected efficacy variables.

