13.1.2 Time to improvement of oxygenation

Oxygen saturation will be measured daily via pulse oximetry.

Time to improvement of oxygenation (in days) is defined as oxygen saturation (pulse oximetry) $>93\%$ and increased by $\geq 1\%$ from Baseline breathing only room air in the 48 hours preceding the measurement.

The time to improvement will be analyzed using a Cox proportional hazards model to estimate the hazard ratio and corresponding 95% CI for SIR1-365 dose vs placebo.

The proportional hazard regression model will include a single term for treatment. Patients without a pulse oximetry $>93\%$ with an increase $\geq 1\%$ from Baseline will be censored at the date of their last pulse oximetry measurement (meeting the preceding 48 hours room air only requirement) or the last date that supplemental oxygen was received, whichever come later.

- Patients without a post-baseline oximetry measurement who did not receive supplemental oxygen will be censored at day 1.
- Death prior to an improvement will be handled as a competing risk event.

The hazard ratio estimation of the event of interest (improvement of oxygenation) will be derived from a cumulative incidence function.

Kaplan Meier curves of time to improvement of oxygenation will be plotted for each treatment group on the same graph.

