13.1.5 Days of hospitalization

Days of hospitalization after treatment will be determined using the ‘Study Drug Administration’ and ‘Hospitalization Details’ eCRFs. The date and time (in format 23:59) of 1st dose of study drug and discharge will be collected.

Duration of hospitalization after treatment up through 14 days will be calculated as

- Duration of hospitalization after treatment (days) = (Date and time of discharge – Date and time of 1st dose of study drug)/60/24

Missing discharge times will be assumed to be ‘23:59’ in order to calculate the maximum duration of time hospitalized. In the event a patient is hospitalized more than 14 days, 14 days will be used for analysis.

For patients that died within the first 14 days while hospitalized, the duration of hospitalization will be imputed as 14 days in order not to underestimate the number of days of hospitalization. In the unlikely event a patient dies within 14 days but subsequent to discharge, the number of days hospitalized will be 14 minus the number of days from discharge to death.

For patients with multiple hospitalizations in the first 14 days, the sum of all intervals will be calculated for analysis.

Duration of hospitalization after treatment as a continuous variable will be summarized descriptively by treatment and analyzed using a 1-way ANOVA model with a single term for treatment.

A similar analysis will be done for the total duration of hospitalization:

- Total duration of hospitalization (days) = (Date and time of discharge – Date and time of admission)/60/24

Missing admission times will be assumed to be ‘00:00’ and missing discharge times will be assumed to be ‘23:59’ in order to calculate the maximum duration of time hospitalized.

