13.3 Exploratory Analysis

As an exploratory analysis, to assess the effect of randomization stratification factors, an ANCOVA model with fixed effects for treatment, Dexamethasone use, and Remdesivir use and the Baseline score and age as continuous covariates will be fitted to the change from Baseline in PaO₂/FiO₂ ratio and CRP values.

The parameter estimates and corresponding P-values for each covariate, the LSMeans (standard error) for each treatment group, the LSMean difference between treatment groups, along with 95% CI of the treatment difference and P-value for treatment comparison will be presented.

The same statistical methods as described for preliminary efficacy endpoints in [Section 13.1.1 PaO₂/FiO₂ ratio](#) and biomarker [in Section 14.1.1 CRP Levels](#) will be followed for the analysis.

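### The models for oxygen-free days, hospital days and time to oxygenation improvement leave out Day 1 respiratory status; they are valid, but give up precision that data already collected could supply

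*SAP*

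**What the plan says.** Three between-arm comparisons contain treatment and nothing else:

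- Oxygen-free days (SAP 13.1.3): "based on an ANOVA model with treatment as fixed effect". The protocol's statistical section specifies the same: "based on a 1-way ANOVA model with a single term for treatment".
- Hospital days (SAP 13.1.5): "analyzed using a 1-way ANOVA model with a single term for treatment".
- Time to improvement of oxygenation (SAP 13.1.2): "The proportional hazard regression model will include a single term for treatment".

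The SAP's covariate rule (12.2) is "Baseline measurement of the respective dependent variable will be used as a covariate", and it applies only to ANCOVA models for selected variables. The models that use it are those for PaO2/FiO2 and CRP. The one model with further covariates (13.3) is fitted "to assess the effect of randomization stratification factors, an ANCOVA model with fixed effects for treatment, Dexamethasone use, and Remdesivir use", plus baseline score and age, and again only for PaO2/FiO2 and CRP.

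SAP section 7 states: "Randomization will be stratified according to age group"; the other two factors are dexamethasone and remdesivir use. There is no oxygen or severity factor.

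The data are in hand. The PaO2/FiO2 ratio is taken "within 30 minutes before dosing on Day 1 as baseline" (Protocol 8.1.1). The schedule of assessments also lists WHO score, oxygen use and pulse oximetry on Day 1.

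**The concern.** Respiratory status at entry can differ between patients. Inclusion criterion 3 can be met by heart rate, respiratory rate or chest imaging, so a patient may enter on room air. Home oxygen is allowed, and so is periodic high-flow oxygen.

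Two of the three endpoints depend directly on that starting state. Oxygen-free days accumulate room-air time from Day 1, so a patient entering on room air starts accruing at once. Oxygenation improvement requires 48 hours on room air and a rise from baseline saturation, so baseline oxygen need affects when the event can occur. For hospital days, baseline status is a prognostic proxy and not a starting value.

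With treatment as the only term, variation explained by entry status stays in the residual. The estimates affected are of the kind that SAP section 6 says the trial will supply for planning. If adjustment is not pre-specified and an imbalance then appears, SAP section 8 would class any adjusted analysis as post hoc.

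**Working it through.** **Inputs from the documents.** About 30 patients per arm, 1:1, two-sided 0.05 (SAP 6 to 8). There is no power, effect size or SD to reproduce, because the sample size was not based on a calculation. Everything below is therefore in SD units.

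**Input assumed.** The correlation r between the Day 1 covariate and the outcome. The documents give none; 0.3 to 0.6 is used as the main range.

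**Duration endpoints: confidence interval.**

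Unadjusted half-width = t(0.975, 58) × sqrt(2/30) = 2.002 × 0.2582 = 0.517 SD.

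Adjusted half-width = t(0.975, 57) × sqrt[(2/30) × (1 − r²) × (1 + 1/56)]. The factor 1 + 1/56, that is 1 + 1/(2n − 4) with n = 30, is the expected penalty for estimating the covariate effect when baseline differs between arms by chance.

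| r | Residual variance removed | Half-width (SD) | Narrower by | Narrower by, ignoring the penalty: 1 − sqrt(1 − r²) |
|---|---|---|---|---|
| 0.2 | 4% | 0.511 | 1% | 2% |
| 0.3 | 9% | 0.498 | 4% | 5% |
| 0.4 | 16% | 0.478 | 7% | 8% |
| 0.5 | 25% | 0.452 | 13% | 13% |
| 0.6 | 36% | 0.417 | 19% | 20% |

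Break-even is where (1 − r²) × 57/56 = 1, so r² = 1/57 and r is about 0.13. At r = 0.5 the gain is worth 30/0.75 = 40 patients per arm before the penalty, and 40 × 56/57, about 39, after it.

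**Duration endpoints: power.** This uses the noncentral t with the same penalty. For a 0.6 SD difference, power is 62.8% unadjusted, 66.0% at r = 0.3 (3 points more) and 74.4% at r = 0.5 (12 points more). The gain depends on the assumed difference. At r = 0.5 it is about 5 points for 0.3 SD and 2.4 points for 1.0 SD, so 0.6 SD lies near the peak. The interval width is the steadier summary, because it needs no effect size.

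**Time-to-event endpoint.** A simulation of 1,500 trials per setting used 30 per arm, exponential times with baseline hazard 0.06 per day, censoring at Day 28, no deaths and one standardised covariate. All of these settings except the arm size and Day 28 are assumed.

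| True conditional HR | Covariate log hazard per SD | Rejection rate, unadjusted | Rejection rate, adjusted | Average HR, unadjusted | Average HR, adjusted |
|---|---|---|---|---|---|
| 1 | 0.5 | 5.7% | 5.1% | 1.00 | 1.00 |
| 1 | 1.0 | 4.9% | 4.9% | 1.00 | 1.01 |
| 2 | 0 | 69.6% | 69.1% | 2.00 | 2.02 |
| 2 | 0.5 | 55.4% | 68.1% | 1.84 | 2.05 |
| 2 | 1.0 | 36.1% | 65.1% | 1.61 | 2.03 |

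Type I error stays near 5% either way. When the covariate matters, leaving it out pulls the hazard ratio toward 1 and costs power. When it does not, adjustment changes almost nothing.

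**The case against.** The strongest reply is that this is an efficiency choice in a Phase 1b safety study. The p-values are there to aid interpretation, and an unadjusted comparison under randomisation is unbiased with a valid interval. That stands.

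A reader might infer that chance imbalance in baseline severity biases these estimates, as a second harm on top of wide intervals. It does not: across randomisations, chance imbalance is part of the sampling variance that the unadjusted interval already covers. A reader might also infer that the SAP breaks its own rule by adjusting PaO2/FiO2 and CRP but not these endpoints. It does not: section 12.2 concerns the baseline of the same variable, and a duration has none.

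Eligibility may also narrow the covariate. Exclusion criterion 1 removes noninvasive ventilation and sustained high-flow oxygen, and low saturation or a low PaO2/FiO2 ratio is among the qualifying signs, so many patients may enter on low-flow oxygen. As an assumed illustration, suppose 10% enter on room air and average 1 within-group SD more oxygen-free days. Then r = sqrt(0.10 × 0.90)/sqrt(1 + 0.10 × 0.90) = 0.30/1.044, about 0.29, where the gain is small.

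Finally, normal-theory figures are approximate here. Oxygen-free days are bounded by the 28-day window, and hospital days after treatment are capped at 14, with in-hospital deaths within 14 days set to 14.

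These points limit the size of the gain. They do not remove it, since the covariate is already collected and the penalty for including it is very small.

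**Conclusion.** The point holds as a loss of precision. All three models omit Day 1 respiratory status, no stratification factor covers it, and no supportive analysis adjusts these endpoints for it. The treatment-only analyses are valid, and nothing here shows bias or an inflated type I error.

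For oxygen-free days and hospital days, the interval would be about 4% to 20% narrower if the baseline-outcome correlation is 0.3 to 0.6. At 0.2 the gain is 1% to 2%, which is negligible. For time to oxygenation improvement, the cost is a hazard ratio nearer to 1 and lower power; its size rests wholly on the simulated covariate effects. A single headline power gain should not be quoted, because the documents give neither an effect size nor a correlation.

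The change is worth making because precision of estimation is part of the stated reason for the sample size, and because it costs little.

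**What to change.** While the SAP can still be amended before unblinding:

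1. Pre-name one covariate for all three models: Day 1 oxygen requirement, room air versus any supplemental oxygen. For these hospitalised patients it is equivalent to baseline WHO score 4 versus 5 and 6 pooled. Pooling is needed because level 6 will be sparse under exclusion criterion 1. With 60 patients, do not enter several correlated severity measures together.
2. In 13.1.3 and 13.1.5, fit ANCOVA with treatment and this covariate. In 13.1.2, add the same term to the model.
3. Report the unadjusted estimate beside each adjusted one, and label the adjusted hazard ratio as conditional on baseline status.
4. State a simple missing-baseline rule that keeps the ITT set whole. For example, use the last value before first dose (before randomisation if untreated), then derive it from the WHO score, then assign the commoner category without reference to arm.
5. Amend SAP section 15, which now reports no changes, because the protocol specifies the one-way ANOVA for oxygen-free days.

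The cost is SAP wording, one degree of freedom and a hazard ratio with a conditional interpretation. No new data are needed.

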13.1.4 WHO ordinal scale

The WHO ordinal scale is a 10-level ordered categorical scale developed by a special committee at WHO to measure illness severity over time. This endpoint will be collected 4 times during the study: at Baseline and on Days 7, 14, and 28.

The scale will be used to assess patients' clinical status during the study. A 2-point reduction on the score of WHO ordinal scale is considered as clinical improvement.

When completing the WHO Ordinal Scale at Day 14/ EOT, if the patient has received physician orders to be discharged from the hospital, the score should be a 3 or less (*no longer hospitalized*).

Change and percentage change from Baseline to Days 7, 14, and 28 in the scores of WHO ordinal scale as a continuous variable will be summarized by visit and treatment.

A separate summary table will be produced, similar to what is described above, summarizing the results at Day 7 (assessments taking place on study day 7), Day 14 (assessments taking place on study day 14) and Day 28 (assessments taking place on study day 28). For any patients with missing Day 7 results, the Day 7 results will be imputed using the last value reported prior to study day 7. Similarly, Day 14 missing observations will be imputed with the last available assessment that took place after study day 7 and prior to study day 14. Day 28 missing observations will be imputed with the last available assessment that took place after study day 14. A summary table will be produced, summarizing these (imputed and reported) results.

Categorical summaries of patients having a clinical improvement during the study (Baseline to Day 28) will be generated presenting the number and percentage of patients with an improvement at any visit from Baseline to Day 28. Associated 95% CI for the proportion of improvement will be provided for each treatment group using the Clopper-Pearson method.

The distribution of outcomes on the ordinal scale will also be plotted using stacked bar charts representing the proportion of patients in each category (uninfected, ambulatory mild disease, hospitalized: moderate disease, hospitalized: severe disease and death), by treatment group over time. A second plot will be produced, similar to what is described above, summarizing the results at Day 7 (assessments taking place on study day 7), Day 14 (assessments taking place on study day 14) and Day 28 (assessments taking place on study day 28). For any patients with missing Day 7 results, the Day 7 results will be imputed using the last value reported prior to study day 7. Similarly, Day 14 missing observations will be imputed with the last available assessment that took place after study day 7 and prior to study day 14. Day 28 missing observations will be imputed with the last available assessment that took place after study day 14.

The mean absolute values and mean absolute change from Baseline up to Day 14, using the actual study day for Day14/EOT assessments, will be plotted per treatment group using line graphs.

13.1.4.1 Time to clinical improvement

Time to clinical improvement is defined as the number of days between the date of first study drug administration and the first date a patient achieves a 2-point reduction on the WHO ordinal scale.

Time to clinical improvement will be analyzed using a Cox proportional hazards model to estimate the hazard ratio and corresponding 95% CI for SIR1-365 dose vs placebo.

The proportional hazard regression model will include a single term for treatment.

- Death prior to clinical improvement will be handled as a competing risk event.
- Patients that do not show any clinical improvement over the assessment period will be censored at the date of last assessment.
- Patients with no post-baseline assessment value will be censored at Day 1.

The hazard ratio estimation of the event of interest (clinical improvement) will be derived from a cumulative incidence function. The Kaplan Meier estimate of median time to event will also be presented for each treatment group.

Table 12.1.4 Categories for WHO Ordinal Scale

Patient State	Descriptor	Score
Uninfected	Uninfected; no viral RNA detected	0
Ambulatory Mild Disease	Asymptomatic; viral RNA detected	1
	Symptomatic; Independent	2
	Symptomatic; Assistance needed	3
Hospitalized: Moderate disease	Hospitalized; no oxygen therapy	4
	Hospitalized; oxygen by mask or nasal prongs	5
Hospitalized: Severe disease	Hospitalized; Oxygen by NIV or High flow	6
	Intubation & mechanical ventilation, $pO_2/FIO_2 \geq 150$ or $SpO_2/FIO_2 \geq 200$	7
	Mechanical ventilation $pO_2/FIO_2 < 150$ ($SpO_2/FIO_2 < 200$) or vasopressors	8

	Mechanical ventilation $pO_2/FIO_2 < 150$ and vasopressors, dialysis or ECMO	9
Death	Dead	10

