#### **8.1.5. Days of Hospitalization**

Hospitalization admission and discharge date and time will be recorded in the eCRF.

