5 STUDY DESIGN AND PLAN

This is a multicenter, randomized, double-blinded, placebo-controlled study to evaluate safety and preliminary efficacy of SIR1-365 in patients with severe COVID-19. The primary objective is to assess the overall safety and tolerability of SIR1-365 administered orally at 100 mg, 3 times per day (TID) for 14 days relative to the placebo group. The secondary objectives are to assess the effects of SIR1-365 on clinical efficacy endpoints and the biomarkers indicative of

inflammation, target engagement, kidney injury and CV endothelial cell damage as well as SIR1-365 pharmacokinetics (PK).

Approximately 60 eligible patients will be randomly assigned at a 1:1 ratio to receive either SIRI-365 at 100 mg, TID or matching placebo for up to 14 consecutive days. For ethical and medical reasons, standard-of-care treatments for COVID-19 will be provided to all patients. Study treatments (either SIRI-365 or matching placebo) will be given as add-on therapy.

Patients could be hospitalized and treated for up to 14 days. Patients will be assessed daily while hospitalized. If the patients are discharged from the hospital before Day 14, all the assessments planned for Day 14 should be carried out before discharge. If a patient is still hospitalized after Day 14, no study drug will be administered after the last dose on Day 14.

It is preferred that the follow-up visit is in person to obtain safety laboratory tests. However, infection control or other restrictions may limit the ability of the patients to return to the clinic. In this case, the follow-up visit may be conducted by phone and only safety data will be obtained. Study drugs will not be administered for early discharged patients. Follow-up visit will be scheduled approximately on Day 28 (± 3) or 14(± 3) days after the last dose for those who are discharged from the hospital before Day 14.

Table 5.1 Treatment Administered

Study drug name:	SIR1-365		Placebo	
Dosage formulation:	Tablets		Matching tablets	
Unit dose strength/Dosage level:	100 mg tablets		NA	
Route of administration	Oral/gastric tube		Oral/gastric tube	
Dosing instructions:	Take 1 tablet three times daily			

Food and water will be allowed as needed.

Study procedures to assess safety, preliminary efficacy, biomarkers, and PK are shown in below table.

Table 5.2 Schedule of Assessments¹²

Days	Screening	Treatment in Hospital								Follow-up Visit/EOS
	-7 to -1	1 ¹	2-6	7	8-9	10	11-13	14 (± 2) /EOT ²		

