10. One blood sample will be collected from each patient within 30 min before and 2 hours (± 5 min) after the 1st dose on Day 1, respectively. On Days 7 and 14, one blood sample will be collected within 30 min before and 2 hours (± 5 min) after the 2nd dose, respectively. Each plasma sample will be divided into 4 parts, 2 for PK analysis and 2 for plasma pRIP1/pMLKL assay conducted at a central lab. PBMC preparation will be done at the sites with necessary equipment according to the laboratory manual for pRIP1/pMLKL assay.
11. About 10 mL of urine sample will be collected before dosing on Day 1, and in the morning on Days 7 and 14 for NGAL and KIM-1 assay to be conducted at a central lab
12. If the patients are discharged from the hospital before Day 14, all the assessments planned for Day 14 should be carried out before discharge. Study drugs will not be administered in early discharged patients. It is preferred that the follow-up visit is in person to obtain safety laboratory tests. However, infection control or other restrictions may limit the ability of the patients to return to the clinic. In this case, the follow-up visit may be conducted by phone and only safety data will be obtained. If a patient is still hospitalized after Day 14, no study drug will be administered after the last dose on Day 14.
13. When completing the WHO Ordinal Scale at Day 14/ EOT, if the subject has received physician orders to be discharged from the hospital, the score should be a 3 or less (*no longer hospitalized*).

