8.4 Early Discharge Assessments

If the patients are discharged from the hospital before Day 14, all the assessments planned for Day 14 should be carried out before discharge.

For all summaries and statistical analyses early discharge assessments will be analyzed and tabulated with Day 14/ EOT.

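### Time to clinical improvement uses a WHO score with a gap between Day 14/EOT and Day 28, so later discharges are dated late, or lost under phone follow-up, although discharge dates are recorded

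*SAP*

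**What the plan says.** SAP 13.1.4.1 counts days from first dose to "the first date a patient achieves a 2-point reduction on the WHO ordinal scale". It fits a Cox model with treatment only and reports a Kaplan-Meier median per group. Death before improvement is a competing event, and a patient who does not improve "will be censored at the date of last assessment". No interval-censored method is named.

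SAP 13.1.4 gives the timing of the score: "This endpoint will be collected 4 times during the study: at Baseline and on Days 7, 14, and 28". Three rules modify it.

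- SAP 8.4 covers early discharge: "If the patients are discharged from the hospital before Day 14, all the assessments planned for Day 14 should be carried out before discharge".
- SAP Table 5.2 gives the Day 14/EOT visit a ±2-day window. Its footnote 13 says that at this visit, "if the subject has received physician orders to be discharged from the hospital, the score should be a 3 or less".
- SAP section 5 sets the last score: "Follow-up visit will be scheduled approximately on Day 28 (± 3" days). It adds that, where a return to the clinic is not possible, "the follow-up visit may be conducted by phone and only safety data will be obtained".

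The discharge date is available independently of the WHO form. Protocol 8.1.5 states: "Hospitalization admission and discharge date and time will be recorded in the eCRF". SAP 13.1.5 already uses that date from the Hospitalization Details eCRF page to compute days in hospital.

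**The concern.** Exclusion criterion 1 keeps out patients on continuous high-flow oxygen, noninvasive ventilation or mechanical ventilation, so a patient on ordinary oxygen enters at score 5. On the scale in SAP 13.1.4.1, scores 4 and above up to death are inpatient states. A 2-point fall from 5 therefore means 3 or less, which is discharge.

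The same clinical event then runs on two clocks. Up to the Day 14/EOT score it carries roughly the date of discharge. After that score it waits for the follow-up visit, or disappears if that visit is a telephone call.

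At stake are the reported medians, the number of improvement events and, to a lesser extent, the hazard ratio. SAP section 6 says the trial should supply estimates for planning later studies, so a median that reflects the visit calendar could mislead that planning.

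**Working it through.** The documents give no effect size, event count or discharge-time distribution for this endpoint, so there is no stated figure to reproduce. The check is date arithmetic from the schedule, followed by illustrations under stated assumptions.

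**1. Which discharges fall in the gap (baseline 5)**

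- Before Day 14: the Day 14 assessments are done before discharge, so the event date is about the discharge date. Day 13 is dated Day 13.
- Day 15 or 16: the Day 14/EOT visit may fall anywhere on Days 12 to 16. If the score is taken at discharge, or with orders already written, the date is right to within a day or so. If the form was completed earlier and without orders, the next score is at follow-up.
- Day 17 onward, no orders at the Day 14/EOT score: always the follow-up visit, Day 28 − 3 = 25 to Day 28 + 3 = 31.

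**2. Delay with in-person follow-up** (visit day minus discharge day)

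| Discharge | Visit on Day 25 | Visit on Day 31 |
|---|---|---|
| Day 17 | 8 | 14 |
| Day 20 | 5 | 11 |
| Day 24 | 1 | 7 |

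**3. Phone follow-up**

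A call that yields safety data only gives no WHO score. The last score is then the one near Day 14, and the patient is censored there without an event, although the discharge date is on file.

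**4. Median** (assumption: lognormal discharge time, placebo median 18 days, log SD 0.5)

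Share of placebo patients discharged by Day 14 = Φ(ln(14/18)/0.5) = Φ(−0.503) = 0.31; by Day 16 = Φ(ln(16/18)/0.5) = Φ(−0.236) = 0.41. Both are below one half, so under the planned dating the Kaplan-Meier curve cannot cross 0.5 before the follow-up visits start on Day 25. Simulations with an 18-day placebo median agree: about 18 to 19 days by discharge date becomes about 25 to 27 days as planned. With exponential medians of 7 to 10 days the median does not change.

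**5. Events lost to phone follow-up** (same assumptions, active median 14 days, arms pooled 1:1)

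- Discharged by Day 28: [Φ(ln(28/18)/0.5) + Φ(ln(28/14)/0.5)]/2 = (0.812 + 0.917)/2 = 0.86.
- By Day 14: (0.308 + 0.500)/2 = 0.40. By Day 16: (0.407 + 0.605)/2 = 0.51.
- With 50% phone follow-up, half of the later discharges are lost. If none of Days 15 to 16 is captured: 0.864 − 0.5 × (0.864 − 0.404) = 0.63. If all are captured: 0.864 − 0.5 × (0.864 − 0.506) = 0.69.

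A separate simulation with exponential times, a 14-day median in both arms and 60% phone follow-up gave 0.75 falling to 0.59.

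**6. Hazard ratio** (simulated, 4,000 per arm, treatment-only Cox model)

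- Lognormal medians 14 and 11 days, log SD 0.4, every discharge after Day 14 dated at follow-up: 1.75 becomes 1.56 in one run and 1.61 in another. With Days 15 to 16 captured: 1.77 to 1.68, and 1.66 to 1.61.
- Lognormal medians 10 and 8 days, log SD 0.6: 1.42 becomes 1.38.
- Exponential times with a true ratio of 1.5: planned estimates of about 1.39 to 1.54. With a true ratio of 1.0 they stay near 1.0.

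For scale, assume about 27 events in each arm of 30. The standard error of the log hazard ratio is √(1/27 + 1/27) = 0.27. The largest shift above is ln(1.75/1.56) = 0.115, or about 0.4 standard errors.

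**The case against.** The strongest reply is that little depends on this analysis. Time to clinical improvement is not among the outcome measures listed in the protocol or in SAP sections 4 and 12.1. The primary outcome is TEAEs, the study is exploratory, and discharge timing is analysed separately in SAP 13.1.5. Both arms share the same visit grid, so no spurious effect arises under the null. All of that stands, and it limits the weight of the point.

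A second reply is that the ±2-day window and the discharge-orders rule rescue discharges just after Day 14. This also stands. A reader might infer that anyone discharged on Day 15 is dated Day 25 to 31. The documents do not support that, because such a patient may be scored on time. Late dating is certain only from Day 17, for a patient scored without orders and then followed up in person.

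Third, Protocol 7.2.1 introduces phone follow-up for patients discharged before Day 14, who have already been scored. SAP section 5 and Protocol 3.1 do not clearly limit it to them, so the loss in step 5 depends on how widely it is used.

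Finally, using the oxygen log to date falls within hospital, such as 6 to 4, would be open to challenge. Exclusion criterion 1 tolerates periodic high flow, so a brief log change could count as improvement that was never scored. The fix leaves those falls on the scored visit.

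**Conclusion.** The gap is real and follows from the documents. For a patient starting at 5, a discharge from Day 17 without orders at the Day 14/EOT score is dated Day 25 to 31, or is not counted at all if follow-up is by phone, while the true date sits in the database. A Day 15 or 16 discharge depends on when the form was completed.

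The harm falls mainly on medians and event counts, and only if recovery is often later than Day 14. The effect on the hazard ratio is modest, well under one standard error at this sample size. All sizes rest on assumed discharge times and phone-follow-up rates.

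Two stronger readings are not supported. One is that the placebo median would jump by about two weeks whenever the true median is near 14 days. That value sits exactly where re-dating starts, so the planned median stayed at 14 or 15 in some runs and became 25 in others. The other is that the treatment comparison is seriously biased, which the simulations do not show. This is a worthwhile, low-cost improvement to a supportive secondary analysis.

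**What to change.** In SAP 13.1.4.1, for patients with a baseline score of 5 or more who have not already improved at a scored visit, date the fall to 3 or less at the live-discharge date on the Hospitalization Details eCRF page. Apply this to patients with phone-only follow-up as well. Keep the scored visit for every other improvement, including 6 to 4 in hospital and any fall from a baseline of 4, where a score of 2 or less is needed and discharge alone does not establish it.

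Use the same derived event in the proportion-improved summary in SAP 13.1.4 (Table 14.2.4.3). Otherwise a Day 20 discharge with phone follow-up would be an event in one table and not in the other.

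The cost is SAP wording and programming, with no new data. The downside is that some event dates are derived rather than read from the WHO form, and the rule that discharge implies 3 or less, now written for the Day 14/EOT visit, is extended to later discharges. State both in the SAP.
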